### 5.3. Multicentre Studies

It is likely that many centres will enrol very small number of participants. Consequently, all centres within the same country will be pooled. In addition, if there are any countries enrolling very small numbers in total (<12 in the Intent to Treat population), these countries will be pooled with another country within a similar geographical region. All amalgamations will be finalised and documented prior to unblinding the treatment arm codes. These amalgamations will be used wherever region is incorporated into an analysis or summary.

In this multicentre global study, enrolment will be presented by centre, country and region (if required).

## 5.4. Examination of Covariates, Other Strata and Subgroups

### 5.4.1. Covariates and Other Strata

Unless otherwise stated, all models used for adherence and rescue free days will allow for fixed effects due to randomised treatment arm, baseline (of the analysis variable), duration of run-in (visits), country, gender, and age (years - determined from screening date). Randomised treatment arm, duration of run-in, country, and gender will be included as categorical covariates; baseline and age will be included as continuous covariates.

The covariates to be considered in the patient reported outcomes (PRO) analyses include randomised treatment arm, age (years - determined from screening date), gender, country and baseline (of the analysis variable), if relevant.

The covariate region will replace country should amalgamation of countries, as described in Section 5.3 Multicentre Studies, be required.

The list of covariates and other strata may be used in descriptive summaries and statistical analyses, some of which may also be used for subgroup analyses.

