## 2. SCHEDULE OF ACTIVITIES (SOA)

Procedures	Screen	Run-In			Treatment Period						EW	Follow -up	Notes
Visit/Contact	V1	V2	V3	V4	V5	V6	V7	V8	V9	V10		V11	
Month of Study	-1	0	0	0	1	2	3	4	5	6			
Day of Study	-28	0	0	0	28	56	84	112	140	168		175	
Visit Window (days)		±2	±2	±2	±2	±7	±7	±7	±7	±7		±2	
Conditional Visits			X	X		X	X	X	X				
SCREENING ASSESSMENTS													
Written Informed Consent	X												Signed by the subject and HCP/ designee prior to any other study assessments. May be completed at a separate visit to screening if required.
Subject Demography	X												
Medical History	X												
Asthma History	X												Including exacerbation history for previous 12 months and those involving hospitalisation
Therapy History	X												Maintenance therapy over previous 12 months, including number of prescriptions requested or provided
Physical Exam	X												Full physical including height, weight and vital signs
Inclusion/Exclusion Criteria	X	X	X	X									ACT assessment for inclusion required at run-in visits
Randomisation		X	X	X									Subject randomised to treatment at only one of V2, V3 or V4 once ACT criteria is met

Procedures	Screen	Run-In			Treatment Period						EW	Follow -up	Notes
Visit/Contact	V1	V2	V3	V4	V5	V6	V7	V8	V9	V10		V11	Conditional Visits: V3 & V4 are only required if a subject is not included at prior run in visit. V6, V7, V8 & V9 are only required for Treatment arms 1 & 3. Randomisation to treatment arms will occur at Visit 2,3 or 4 when randomisation criteria have been met
Month of Study	-1	0	0	0	1	2	3	4	5	6			
Day of Study	-28	0	0	0	28	56	84	112	140	168		175	
Visit Window (days)		±2	±2	±2	±2	±7	±7	±7	±7	±7		±2	
Conditional Visits			X	X		X	X	X	X				
SAFETY ASSESSMENTS													
Concomitant Medication		X											
Urine Pregnancy Test	X	X	X	X	X					X	X		
SAEs	X					X							
Non-Serious Adverse Events that leads to withdrawal	X					X							Non-serious adverse events that leads to dose modification, drug discontinuation, or withdrawal from the trial. Collected from start of run in
Non-serious Adverse Drug Reactions	X					X							Collected from start of run in
Exacerbations	X					X							Severe Exacerbation are to be reviewed and recorded. Collected from start of run in
Unscheduled HCP visits						X							All secondary care contacts and all primary care contacts related to Asthma
QUESTIONNAIRES & Patient Reported Outcomes (PROs) (Performed in the order given here)													

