#### 3.1. Study Rationale

This study will be the first to evaluate the effect of the CIS on adherence to maintenance therapy (Relvar/Breo ELLIPTA) in uncontrolled asthmatic patients (Asthma Control Test [ACT] <20 at the screening visit and ACT <20 at a subsequent randomisation visit after run-in). The run-in exists to ensure a stable level of control prior to entry into the study, given the possible change in treatment and is described in detail in Section [5.1](#).

The study has been designed to assess how the CIS impacts adherence of asthmatic patients to maintenance therapy, when both the subject and the HCP receive data on adherence from the sensor on the patient's Relvar/Breo ELLIPTA maintenance therapy.

In addition, the five treatment arms of the study will allow evaluation of different elements of the CIS. These include; having additional data provided from a sensor on

rescue medication and the effect of the patient alone seeing any data with no data shared to the HCP, or both the patient and HCP seeing the data from the sensors. See Section 5, Section 7 and Table 1 for details on the 5 arms. Furthermore, this study will provide preliminary data evaluating the effect of the CIS on patient outcomes, including rescue medication use, change in ACT and patient reported outcomes (PROs).

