### **Conditional Visits 2, 3 and 4 (V2, V3 and V4)**

At the end of each month of the flexible run-in period, ACT will be re-assessed at the clinical centre. If at the first monthly visit of the flexible run-in the subject's ACT is <20 (uncontrolled) then the subject will be randomised to study treatment and subsequent run-

in visits are not required. Subjects with an ACT of  $\geq 20$  at V2 or V3 repeat the month run-in period. However, subjects who have an ACT  $\geq 20$  at all 3 visits, during the flexible run-in, will not be randomised and will be registered as a run-in failure.

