### Assignment of Randomisation Number

At V2, V3 or V4 (Run-in visits), subjects meeting the eligibility criteria will be assigned to study treatment using an interactive web response system (IWRS) that will be used by HCP or designee to register the subject, randomise the subject and provide treatment assignment information. Details on how to use RAMOS NG, the IWRS, to register and randomise subjects is provided in the RAMOS NG IWRS manual and SRM.

Once a randomisation number has been assigned to a subject, it cannot be reassigned to any other subject in the study.

Subjects will be assigned to study treatment in accordance with the randomisation schedule. The randomisation code will be generated by GSK using a validated computerised system. A subject will be randomised using RAMOS NG. The study will use central-based randomisation system to allocate treatments.

Subjects will be randomized 1:1:1:1:1 to one of the five treatments arms for the duration of the treatment period. See Section 5 for description and numbering of arms.

Each investigator will be provided with sufficient study supplies to respond directly to subject requests for study treatment as required. Additional supplies will be supplied as needed to the sites. Details of how to use the IWRS system (RAMOS NG) to randomise subjects and manage study treatment supplies (including dispensing) is provided in the RAMOS NG IWRS manual and SRM.

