### **7.2.3.4. Statistical Analyses / Methodology Specification**

Details of the planned displays will be provided in [10.8 Appendix 8: List of Data Displays](#) and will be based on GSK data standards and statistical principles.

Unless otherwise specified, endpoints/variables defined in Section [7.2.3.1](#) Summary Measure will be summarised using descriptive statistics, graphically presented (where appropriate) and listed.

### 7.2.3.4.1. Change from baseline in ACT total score at month 6

Endpoint / Variables
Change from baseline in ACT total score Month 6 (visit 10)
Model Specification

This endpoint will be analysed using a mixed model repeated measures (MMRM) model utilising the REML estimation approach and the default unstructured covariance matrix structure. Whilst missing data are not implicitly imputed in this analysis, there is an underlying assumption that the data are MAR. All non-missing data for a participant will be used within the analysis and, via modelling of the within-participant correlation structure, the derived treatment differences will be adjusted to take into account missing data.

Terms fitted in the model will include:
 
 
Dependent Variable: change from baseline in ACT total score
 
Covariates: 
 
Fixed categorical: randomised treatment arm, visit (month 1 and 6), gender and country.
 
Fixed continuous: baseline ACT total score and age
 
Interaction terms: randomised treatment arm-by-visit, baseline ACT total score-by-visit
 
Random effect: participant
 
 
 

Model Checking & Diagnostics

 
If this model fails to converge, alternative correlation structures may be considered
 
Appropriate graphs will be reviewed as part of the model checking process to ensure that distributional assumptions hold. These will include a normal probability plot of the residuals and a plot of the residuals versus the fitted values (checking the normality assumption and constant variance assumption of the model, respectively).
 
Interactions with treatment will be explored for other model covariates and tests for interactions will be at the 2-sided 10% significance level. Any significant interactions that are found will be thoroughly investigated and where necessary, extra outputs will be produced.
 

Model Results Presentation

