Adjusted mean change from baseline values for each treatment arm will be presented with their associated standard errors. The estimated treatment difference along with corresponding standard error, 95% confidence interval (CI) and p-value will be presented for the treatment comparisons at month 6 (Visit 10).

### 7.2.3.4.2. ACT total score $\geq 20$ at month 6

Endpoint / Variables
Percentage of patients becoming controlled as defined as an Asthma Control Test score $\geq 20$ at Month 6 (Visit 10)
Model Specification

This endpoint will be analysed using a logistic regression model. Only the month 6 (visit 10) data will be included in the model. Month 1 (visit 5) data will not be implemented since by this timepoint participants may not have reverted to steady medicating behaviour.

Will not be included since participants may not have reverted to normally medicating practise within one month's use of the CIS/

Terms in the model:
 
 
Dependent variable: ACT total score <math>\geq 20</math> responder/non-responder at month 6 (binary score)
 

- Covariates:
  - Categorical: randomised treatment arm, gender and country
  - Continuous: baseline ACT total score and age.

Patients who have a missing ACT total score at month 6 (visit 10) (i.e. no ACT data on-treatment) will be classified as non-responders at that visit.

Computation of confidence intervals for the odds ratios is based in the individual Wald tests.

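### The four ACT models leave out run-in visits, an already derived and probably prognostic covariate; this causes no bias, and adding it is a small, nearly free improvement

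*SAP*

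**What the plan says.** **Entry rule.** Protocol 5.1 (Conditional Visits 2, 3 and 4): "If at the first monthly visit of the flexible run-in the subject's ACT is <20 (uncontrolled) then the subject will be randomised". Those who score 20 or more "at V2 or V3 repeat the month run-in period"; only a score of 20 or more at all three visits is a run-in failure. The Schedule of Activities agrees: "Subject randomised to treatment at only one of V2, V3 or V4 once ACT criteria is met".

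**Allocation.** Protocol 7.5: "Subjects will be randomized 1:1:1:1:1 to one of the five treatments arms for the duration of the treatment period". This happens at the visit where the ACT criterion is met. No stratification by run-in length is described.

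**Covariates.** SAP 5.4.1 puts duration of run-in (visits, categorical) in the adherence and rescue-free-days models. For patient-reported outcomes it says "The covariates to be considered in the patient reported outcomes (PRO) analyses include randomised treatment arm, age", then gender, country and baseline. The ACT mixed model (SAP 7.2.3.4.1) has "Fixed categorical: randomised treatment arm, visit (month 1 and 6), gender and country", plus baseline ACT, age and two interactions with visit. Each of the three ACT logistic models (7.2.3.4.2 to 7.2.3.4.4) has "Categorical: randomised treatment arm, gender and country", plus baseline ACT and age.

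**Change table.** SAP Table 1 says that run-in duration enters the analysis models as a categorical covariate and does not limit this to adherence or rescue use. Protocol 11.4 lists age, sex, region and baseline, and allows other covariates where appropriate.

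**The concern.** Run-in visits record a participant's recent ACT history. Someone randomised at V2 has scored below 20 at both V1 and V2. Someone randomised at V3 or V4 has scored 20 or more once or twice in the preceding months, and so has already met one of the ACT responder thresholds during run-in. Baseline ACT is one score at the randomisation visit (SAP 5.2), so a 19 at V2 and a 19 at V4 after two scores of 20 or more enter the models as the same value. Because scores vary from month to month, the two groups can be expected to differ at Month 6 even at equal baseline.

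The SAP adjusts for run-in visits where the variable is not built from the outcome, and omits it where it is. At stake is some precision, and the handling of chance imbalance, in four secondary analyses: change in ACT, ACT of 20 or more, a gain of 3 or more, and the composite.

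**Working it through.** **The plan's own figures.** There is none for ACT: the documents give no ACT SD, within-person correlation, run-in gain or expected V3/V4 share. The sample-size figures concern adherence and do reproduce. With 76 per arm, difference 15, SD 28 and two-sided 5%, power is 0.910 (normal) or 0.907 (t), against a stated 90%; 380/0.88 = 432 randomised.

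**Simulation of the run-in rule.** Taken from the protocol: eligible if V1 is below 20, randomised at the first of V2, V3 or V4 below 20, scores limited to 5–25. Assumed: ACT mean 16, a run-in gain of 1.5 points, normal between- and within-person variation with the SDs shown, and month-to-month autocorrelation ρ of the within-person part. Month 6 ACT is regressed on baseline ACT with and without an indicator for V3/V4 entry.

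| SD between / within | ρ | OR, ACT ≥20 | Points at equal baseline | Fall in residual variance |
|---|---|---|---|---|
| 3.3 / 2.2 | 0 | 2.6 | 1.7 | about 4% |
| 3.3 / 2.2 | 0.5 | 1.7 | 1.0 | 1.0% |
| 3.3 / 2.2 | 0.8 | 1.3 | 0.4 | 0.2% |
| 2.5 / 3 | 0.8 | 1.2 | 0.3 | 0.1% |

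With ρ = 0 and other inputs varied (mean 15–17, SDs 3–3.5 and 2–2.5, gain 1–2), the odds ratio is 2.3–2.9, the difference 1.5–1.8 points, the variance reduction 4.1–4.5% and the V3/V4 share 12–22%. A separate run also had no autocorrelation beyond a constant within-person correlation (total SD 4, mean 15–19, correlation 0.4–0.7) and coded V3 and V4 separately. It gave 0.9–1.9 points for V3 and 1.4–2.7 for V4, odds ratios of 1.5–2.8 and 2.1–4.4, and a variance reduction of about 2–5%. The high V4 values apply to few people: 64–94% enter at V2.

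**Precision.** A 4.5% fall in variance multiplies the standard error by √(1 − 0.045) = 0.977. It is worth 76/0.955 ≈ 80 per arm instead of 76. At 0.1% the gain is nil: 76/0.999 = 76.1.

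**Chance imbalance.** There are 432/5 ≈ 86 per arm. With a 20% V3/V4 share, the SD of the between-arm difference in that share is √(2 × 0.2 × 0.8/86) = 0.061. Multiplied by 0.3 to 1.7 points, this gives a typical shift of 0.02 to 0.10 ACT points. With a residual SD of about 2.9, the standard error of an arm difference is 2.9 × √(2/86) = 0.44, so the shift is at most about a quarter of a standard error. The minimally important difference is 3 points (Protocol 9.1.3.1).

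**The case against.** The strongest reply is that nothing here is an error. Allocation follows the run-in, so omitting a pre-randomisation covariate cannot bias the comparison, and chance imbalance is already reflected in the standard error. The ACT comparisons are secondary and descriptive with no formal inference planned (Protocol 11.1, SAP 2.4). The SAP's list follows Protocol 11.4, and run-in duration appears in the protocol only for the adherence model. Baseline ACT also captures part of the difference: in simulation V3/V4 entrants average about 17–18.5 at baseline and V2 entrants about 14–15.5. All of this stands. What remains is that adjusted estimates, confidence intervals and p-values will be reported, the variable is already derived, and no reason is given for leaving it out.

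Four stronger readings are tempting and are not supported:

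- *Run-in visits are a strong predictor of ACT.* The documents contain no data on this, and the simulated association fades as autocorrelation rises.
- *V3/V4 entrants return to 20 or above whatever their arm.* Even with no autocorrelation only 37–43% do so at Month 6, against 11–20% of V2 entrants. A score below 20 after a higher one may also be real deterioration.
- *The asthma-control objective is formally tested and therefore compromised.* It is descriptive.
- *The run-in defeats its own purpose.* Protocol 3.1 says "The run-in exists to ensure a stable level of control prior to entry into the study", but ties this to the possible change of treatment, and Protocol 5.4 gives the aim as assessing the effect of that change or of being in the study. A covariate would not cure a design complaint in any case.

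**Conclusion.** The omission is real and unexplained, but it is a missed small improvement and not a flaw in the comparison. Run-in visits are likely to be prognostic for ACT because they are built from earlier ACT values. Under assumed inputs, V3/V4 entry carries an odds ratio for ACT of 20 or more of about 1.2 to 2.9 and 0.3 to 1.7 points at equal baseline; adjusting for it lowers residual variance by about 0.1 to 4.5%. The upper ends need independent monthly errors and the lower ends an autocorrelation of 0.8; the documents do not say which is nearer the truth. Particular no-autocorrelation scenarios, and V4 coded alone, go somewhat higher. No conclusion about asthma control would plausibly turn on this. The mismatch between SAP Table 1 and SAP 5.4.1 is a wording point, but it does leave the intended ACT model unclear.

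**What to change.** In SAP 5.4.1 and 7.2.3.4.1 to 7.2.3.4.4, add duration of run-in (visits), categorical as in the adherence models, to the ACT mixed model and the three ACT logistic models. State in advance that V3 and V4 will be merged if either is sparse. Align SAP Table 1 with 5.4.1 so that both name the same models. If the sponsor prefers to leave the term out, give the reason in one sentence and limit the Table 1 wording to adherence and rescue-free days.

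Cost: at most two degrees of freedom per model, no new data and no protocol change, since Protocol 11.4 allows it. The logistic odds ratios become conditional on one more covariate and will change slightly. Make the change before the treatment codes are released; added after results are seen, the term would be post hoc.

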### 5.4.2. Examination of Subgroups

The following outcomes will be summarized by randomised treatment arm within subgroups defined by country.

- Enrollment
- Demographic characteristics
- Ellipta adherence

For these summaries, subgroups will be defined as in [Table 2](#).

**Table 2**

Category	Subgroups
Country	
 
• US, Canada, Germany, Italy, Netherlands, Spain, UK
 

Baseline ACT total score	
 
• <=15, 16 - 19
 

Age (years – as determine from screening date)	
 
• 18-35, 36-48, 49-58, >58 years
 

Notes: Details of the planned summaries are presented in Section [10.8 Appendix 8: List of Data Displays](#)

## 5.5. Multiple Comparisons and Multiplicity

No adjustments for multiplicity will be applied.

## 5.6. Other Considerations for Data Analyses and Data Handling Conventions

Other considerations for data analyses and data handling conventions are outlined in the appendices:

Section	Component
10.1	Appendix 1 : Schedule of Activities
10.2	Appendix 2 : Assessment Windows
10.3	Appendix 3 : Study Phases and Treatment Emergent Adverse Events
10.4	Appendix 4 : Data Display Standards & Handling Conventions
10.5	Appendix 5 : Derived and Transformed Data
10.6	Appendix 6 : Reporting Standards for Missing Data
10.7	Appendix 7 : Abbreviations & Trade Marks
10.8	Appendix 8 : List of Data Displays

## 6. STUDY POPULATION ANALYSES

### 6.1. Overview of Planned Study Population Analyses

Study population summaries will be based on the ITT population, unless otherwise specified.

Study population displays including summaries and lists of study populations, screening and run-in status, participant study and study drug disposition, participant enrolment, inclusion and exclusion and important protocol deviations, demographic, age, race and baseline characteristics (including height, weight and BMI), medical conditions, family and smoking history and prior and concomitant medications will be based on GSK Core Data Standards. Details of the planned displays are presented in Section [10.8 Appendix 8: List of Data Displays](#).

Concomitant medications will be coded using the GSK Drug coding dictionary. Summaries of the number and percentage of participants taking concomitant medications will be displayed by ingredient without regard to Anatomical Therapeutical Chemical (ATC) classifications. These summaries will include single-ingredient medications and will present multi-ingredient medications according to the combination of the component ingredients. Summaries will be split into asthma and non-asthma concomitant medications, as well as into those taken pre-screening, during run-in, whilst on-treatment and post-treatment (as described in Section [10.3.1 Study Phases](#)).

Asthma maintenance concomitant medications taken by participants in the 12 months prior to screening (pre-screening) will also be summarised as well as those used to treat severe exacerbations experienced whilst on study.

### 6.2. Supplementary Information for Study Population Displays

#### 6.2.1. Disease and Baseline Characteristics

Summary of attendance at each scheduled clinic visit will be presented.

Summaries and lists of the Relvar/Breo ELLIPTA and Salbutamol MDI sensor statuses as well as the App status during the study will be presented.

Asthma exacerbation history (12-month history) at screening will be summarised with frequency distributions of the number of exacerbations treated with oral/systemic corticosteroids not involving hospitalization; the number of exacerbations treated without oral/systemic corticosteroids not involving hospitalization; the number of exacerbations requiring hospitalization; and the total number of exacerbations (i.e., those not involving hospitalization and those involving hospitalization).

Asthma duration will also be summarised.

The screening and baseline lung function test and exhaled nitric oxide summaries will include screening (Visit 1) pre-bronchodilator and pre-ICS/LABA, PEF (in litres per minute (L/min)) and FeNO (millilitres per second (mL/sec)). Baseline PEF (L/min) and

FeNO (mL/sec) measured at Randomisation (Visit 2/3/4) will also be summarised. Additionally, screening and baseline PEF will be summarised by country.

Prescription details (12-month history) at screening will be summarised with frequency distributions of the number of asthma maintenance therapy prescriptions requested or prescribed; the number of asthma maintenance therapy requested or prescribed that would need to be 100% compliant. Compliance in the previous 12 months will be calculated as  $100 * (\text{Actual number of prescriptions}) / (\text{Number of prescriptions needed to be 100% compliant})$  and summarised. These data will also be listed.

